5.5 RANDOMIZATION AND BLINDING

After returning the baseline survey, we will randomize respondents in a 1:1 fashion to intervention or control, stratified by site. To randomize a patient, the Project Director will log onto the study's database system (which will be adapted from the one used in [name] previous studies), enter the subject's unique study ID, confirm eligibility, and confirm that the survey has been received. The database system verifies that all randomization criteria have been satisfied, then assigns a study ID and a group to the subject. The database system will automatically input the date of randomization and the participant's assignment into their study record. The study's Project Director and counselors will have access to treatment assignments. The study's research assistants and our biochemical validation company (Salimetrics, described in section 4.0) will be kept blind to treatment assignments. Intervention participants will be aware of the arm to which they are assigned when they receive the first phone call from a study counselor.

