We anticipate low, but potentially important rates of survey non-response to all or part of the 6- and 12-month surveys. We will use the evidence-based recruitment strategies described above (incentives, reminders, mixed mode survey administration) to minimize non-response. A common practice in smoking cessation research is to treat non-respondents at follow-up as continuing smokers (i.e., intent to treat). This practice is perceived to be a conservative approach but does not, in fact, produce valid estimates of quit rates.³³ We will use multiple imputations to fully use available baseline information and partial later surveys. We will use a propensity-based multiple imputation method similar to that discussed by Little³⁴ using separate imputation procedures within each study group and design stratum combination. Within a given combination, we will estimate the propensity for responding to cotinine validated abstinence for each individual from a logistic regression model for survey response using the characteristics measured at baseline as explanatory measures. Within a combination of intervention and design strata, we will further stratify the sample according to the values for these estimated propensities. Within a propensity substratum, we will impute a value for the outcome measure for each non-respondent by randomly sampling an outcome value from the respondent values in the substratum. Multiple completed datasets will be created and the point estimates and the estimated standard error from each dataset will be combined to arrive at a single point estimate (using the specific method discussed below), its estimated standard error, and the associated confidence interval or significance test. This approach assumes that missing outcome data due to non-response is missing at random.

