The power analysis is based on the primary outcome – cotinine-validated abstinence at 12-month follow-up. Our data is stratified on four hospital sites. Considering that a stratified random sample is usually more efficient than a simple random sample, to be conservative, we assume the two groups are two independent simple random samples in the following power analysis. Based on response rates during the first quarter of recruitment, we expect to receive completed surveys from 20-25% of the 20,000 patients receiving the initial mailing and 85% of respondents will be eligible (i.e., report smoking cigarettes in the prior 30 days). We will send initial mailings until we receive completed surveys from 3,840 eligible patients who will be randomly assigned to intervention and control and comprise the study population. We estimate the quit rate in the control group will be 4%. In the intervention group, about 20% of the people will accept our offer of telephone treatment, based on [name] data. We anticipate that the quit rate among Veterans

enrolled in counseling will be 16%. We are using a more conservative estimate from what we found in our recently-completed reactive recruitment study (20%) because participants will not have been directly referred from a healthcare provider. When the treatment cessation rate is combined with that from patients who do not accept treatment (assuming also a 4% quit rate), there will be a population-level quit rate of 6.4% in the intervention group, which gives us a 90% chance to detect a difference between the two groups.

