The table below shows the detectable increases in anticipated long-term abstinence rate for the intervention group for power = 0.75, 0.80, 0.85, 0.90, based on two sided two independent proportions test with type I error of $\alpha=0.05$. We varied the anticipated long-term abstinence rate in the control group from 3% to 4%. (We used Pass 2008 NCSS software for the calculation.) As an example, the proposed sample size provides 80% power to detect any increase greater than 2.0% in population-level abstinence rate for the intervention group when the abstinence rate in the control group is 4%, a small but clinically-meaningful quit rate that results in overall cost-savings.³⁸ Reversing the calculation and solving for the quit rate for people who accept counseling, if the underlying quit rate is 4% and we get 20% of intervention patients to enroll in counseling (N=384), we will have 80% power to detect a difference if the success rate at counseling is as low as 14%.

Note that a lower response rate on the baseline survey does not affect our power. Since we randomize after response, we can mail additional surveys until we have 3,840 respondents. A recruitment cohort of 20,000 patients and enrolled sample of 3,840 participants therefore gives us some safety margin, to allow for variability in:

- The treatment engagement rate
- The rate of success at counseling (i.e., if less than 16%)
- If the success rate among intervention patients who do not enroll in counseling is <4% (which is conceivable, since these are the people who declined to enroll in telephone counseling).

Table 1: Statistical Power Analysis (1920 baseline survey respondents per group) for Abstinence Rates

| Control group P1 | Power | Intervention group P2 | Difference P2-P1 | Odds Ratio |
|------------------|-------|-----------------------|------------------|------------|
| 0.03 | 0.95 | 0.053 | 0.023 | 1.82 |
| 0.03 | 0.90 | 0.051 | 0.021 | 1.72 |
| 0.03 | 0.85 | 0.049 | 0.019 | 1.66 |
| 0.03 | 0.80 | 0.047 | 0.017 | 1.61 |
| 0.03 | 0.75 | 0.046 | 0.016 | 1.57 |
| 0.04 | 0.95 | 0.066 | 0.026 | 1.70 |
| 0.04 | 0.90 | 0.063 | 0.023 | 1.62 |
| 0.04 | 0.85 | 0.061 | 0.021 | 1.56 |
| 0.04 | 0.80 | 0.060 | 0.020 | 1.52 |
| 0.04 | 0.75 | 0.058 | 0.018 | 1.49 |

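### The hot-deck imputation omits uncertainty about the donor distribution, so pooled standard errors are too small: negligible at about 10% missing, material from roughly 25%

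*Combined protocol and SAP*

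**What the plan says.** The Missing Data part of section 6.0 rejects counting non-respondents as smokers and adopts propensity-based hot-deck multiple imputation, done separately in each combination of study group and design stratum. Respondents and non-respondents are sub-stratified by estimated response propensity, and each missing outcome is filled "by randomly sampling an outcome value from the respondent values in the substratum". Several completed datasets are made, and "the point estimates and the estimated standard error from each dataset will be combined" into one estimate, standard error and confidence interval or test.

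The plan describes no resampling of donors and no draw of the substratum rate. The number of imputations and the combining rule are not given. The method is said to resemble a cited hot-deck procedure.

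On the amount of missing data there is one statement: "We anticipate low, but potentially important rates of survey non-response". No figure follows. The same section applies the imputation to missing cotinine validation as well.

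The primary comparison is exact logistic regression accounting for site. The plan does not say how exact results are pooled over imputed datasets.

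**The concern.** Multiple imputation gives valid standard errors only if the spread between imputations reflects everything unknown about the missing values. Two things are unknown here: which value each non-respondent would have had, given the substratum's abstinence rate, and the rate itself, which is estimated from a finite set of respondents. Drawing repeatedly from the same respondents captures the first and omits the second. The between-imputation variance is then too small, and so is the pooled variance.

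This is the main missing-data method for the primary outcome. If the shortfall is large enough, the confidence interval for the abstinence comparison is too narrow and a nominal 5% test rejects too often. The pattern-mixture sensitivity analyses do not repair this: the model sketched for them shifts the donor distribution and feeds it into the same imputation process.

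**Working it through.** **Inputs from the documents**
- Size of trial: "1920 baseline survey respondents per group" (Table 1).
- Allocation: "we will randomize respondents in a 1:1 fashion to intervention or control, stratified by site" (section 5.5), with four sites (section 5.2).
- Power calculation: "based on two sided two independent proportions test with type I error of" 0.05.
- Rates: 4% control and 6.4% intervention. The second is 0.20 × 16% + 0.80 × 4% = 3.2% + 3.2% = 6.4%.

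**Assumed, because the plan does not state them:** missing fraction f from 5% to 40%; Rubin's rules for pooling; 5, 20 or very many imputations; five propensity substrata per arm and site.

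**1. The plan's own figure.** The plan states a "population-level quit rate of 6.4% in the intervention group, which gives us a 90% chance to detect" a difference. A two-proportion calculation with 1,920 per arm gives 91.8% (90% power needs 1,797 per arm). For 4% against 6.0% it gives 81.2%, against 80% stated. All ten rows of Table 1 reproduce within 2 points. These power figures contain no allowance for imputation, so they neither support nor contradict the point.

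**2. Variance of the planned hot deck.** Take n people with outcome variance S², of whom a fraction f is missing, and many imputations.
- Within-imputation variance: S²/n.
- Between-imputation variance with fixed donors: f² × S²/(fn) = f·S²/n.
- Pooled variance: (S²/n)(1 + f).
- True variance: the estimate converges to the respondents' mean, so S²/[n(1 − f)].
- Ratio of pooled to true: (1 + f)(1 − f) = 1 − f².

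The size of a two-sided 5% test is then 2Φ(−1.96·√(1 − f²)).

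| f | 1 − f² | SE too small by | Size |
|---|---|---|---|
| 5% | 0.9975 | 0.1% | 5.03% |
| 10% | 0.99 | 0.5% | 5.12% |
| 15% | 0.9775 | 1.1% | 5.26% |
| 20% | 0.96 | 2.0% | 5.48% |
| 25% | 0.9375 | 3.2% | 5.77% |
| 30% | 0.91 | 4.6% | 6.15% |
| 40% | 0.84 | 8.3% | 7.24% |

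**3. Variance with donors bootstrapped first.** The donor mean now varies between imputations with variance S²/[n(1 − f)]. The between-imputation variance becomes (S²/n)[f + f²/(1 − f)] = (S²/n)·f/(1 − f). The pooled variance is (S²/n)[1 + f/(1 − f)] = S²/[n(1 − f)], which is the true variance.

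**4. Simulation in the plan's structure.** Two arms, four sites, five substrata of 96, mean abstinence 4%, no treatment effect, site-stratified Mantel-Haenszel log odds ratio, Rubin pooling with a t reference, 5 or 20 imputations, 40,000 trials per setting (Monte Carlo SE about 0.1 point). Size with complete data was 4.8%.

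| f | Planned hot deck, equal or unequal missingness across substrata | Planned hot deck, unequal only | Donor bootstrap, unequal only |
|---|---|---|---|
| 10% | 5.0–5.2% | 5.0–5.2% | 4.8–5.0% |
| 20% | 5.3–5.5% | 5.3% | 4.7–4.8% |
| 25% | 5.6–6.0% | 5.8–6.0% | 4.9–5.0% |
| 30% | 6.0–6.4% | 6.2–6.4% | 5.1–5.2% |
| 40% | 6.9–8.2% | 8.1–8.2% | 5.2–5.6% |

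The simulation agrees with the formula. At 40%, unequal missingness makes the shortfall larger, because it grows with the square of the missing fraction in each substratum.

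**The case against.** **The plan expects little missing data.** At 10% missing or less the size is practically 5%, and follow-up is well supported: up to ten calls, a mailed fallback, payments, and a second saliva kit with reminders. This stands and limits the point. It does not close it, because the plan's word for low missingness refers to surveys, whereas the primary outcome also needs a mailed saliva sample (section 5.7.4). Only people reporting abstinence are sent a kit, so the addition may be modest. If 10% report abstinence and half of those return nothing (both assumed), it adds 0.10 × 0.50 = 5 percentage points. People who report abstinence but use nicotine replacement are not eligible for verification at all. Rates of 25% or more are therefore not excluded, but nothing in the documents points to them.

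**The primary test is exact, hence conservative.** Fisher's test on complete data, 1,920 per arm at 4%, has an actual size of 4.1%. If that carried through pooling, scaling its critical value by √(1 − f²) would give about 4.5% at 20% missing, 4.8% at 25% and 5.1% at 30%. That is a fair possibility, but the 4.1% belongs to a single complete table. Pooling estimates and standard errors leads to a test of estimate over standard error. The plan does not say which applies.

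**The cited procedure may resample donors.** That cannot be checked here. The plan claims only similarity to it, and a statistician following the plan's own text would code the plain draw.

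**A stronger reading on saliva.** A reader might infer that reported quitters without saliva will be matched only to reported quitters with saliva, which would concentrate the missingness where the outcome varies. Assume 8% report abstinence, half of them are confirmed, 10% do not answer the survey and 60% of kits come back. Then 0.10 + 0.90 × 0.08 × 0.40 = 12.9% of people are missing, and simulated size was about 6.8%. The plan does not describe such matching: its substrata come from baseline characteristics, although it also speaks of using partial later surveys. The conclusion does not rest on this reading.

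**Conclusion.** The point holds in a limited form. As described, the imputation is improper, and the pooled standard error is too small by a factor of about √(1 − f²). This is negligible up to about 10% missing, small at 20% and material from roughly 25%.

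A reader might infer that the primary test exceeds its 5% level. The documents do not support that: they give no missing rate, they describe survey non-response as low, and they leave open how the exact analysis is pooled. What they support is that size can exceed 5%, by an amount that depends on the missing rate.

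The figures assume Rubin's rules, the same missing fraction in both arms, and outcomes missing at random within substrata. The simulation treated the propensity substrata as known, so error in estimating them is not included.

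Severity is minor and confidence moderate.

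**What to change.** Add an approximate Bayesian bootstrap step to the Missing Data text: for each imputation, first draw a bootstrap sample of the respondents in the substratum, then draw donors for the non-respondents from that sample. The stratification and the propensity model stay as they are.

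In the same place, state the number of imputations and the rule for combining results with the site-stratified primary analysis, including whether the pooled test remains exact or becomes a test of estimate over standard error. The bootstrap step alone does not settle that.

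The cost is a few sentences in the plan and a line of code, with no extra participants or data. The downside is slightly wider confidence intervals, by about 0.5% at 10% missing (1/√0.99 = 1.005) and about 5% at 30% (1/√0.91 = 1.048). The change should be made before outcome data are seen by arm.

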5.7 DATA COLLECTION

All participants will be surveyed by mail at baseline, by mail 2 weeks after enrollment, and by telephone (or mail for non-respondents) at 6 and 12 months from enrollment. Research assistants will make up to 10 attempts at different days and times to reach participants by phone for the 6 and 12 month surveys. If we cannot reach a participant after 10 attempts, we will mail a paper version of the survey with a cover letter (Appendix K) to participants. Patients will receive a \$10 payment as reimbursement for completing each survey.

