5.7.1 Baseline Survey

Smoking questions

- Smoking habits and history.* We will use measures adapted from the California Tobacco Survey¹⁵ that we have used in several previous studies to assess the number of cigarettes smoked per day, number of days smoking per week, and nicotine dependence..¹⁶
- Motivation.* We will assess readiness for change using the Stage of Change scale.¹⁷
- Tobacco treatment used in prior 12 months.* We will ask participants to indicate whether a VA provider talked to them about smoking in the prior 12 months and which tobacco treatments they used in the prior 12 months.
- Health.* We will ask a single item asking participants to rate their general level of health on a 5-point Likert type scale.

5.7.2 2-Week Survey

Sociodemographics

- Demographics.* Age, sex, marital/partnership status, race/ethnicity, education, and occupation will be assessed, as well as text messaging interest and capabilities.
- Environment.* Using questions from the California Tobacco Survey¹⁵ we will assess household tobacco use and restrictions on smoking at home.

Smoking questions

- Smoking habits and history.* We will use measures adapted from the California Tobacco Survey¹⁵ that we have used in several previous studies.
- Self-Efficacy.* Self-efficacy for smoking cessation will be measured with the 14-item Confidence Questionnaire Form¹⁸ which assesses smoking cessation self-efficacy across 14 different situations or mood states.
- Pros and Cons.* We will use the 6-item decisional balance scale which measures positive and negative attitudes toward quitting.¹⁹
- Perceptions regarding tobacco use.* We will also assess perceived control over withdrawal symptoms⁷⁴ and perceived antismoking norms,²⁰⁻²⁴ measures that predict tobacco use.

Health questions

- ❑ *Health habits.* We will use the AUDIT-C^{24,25} to assess alcohol use and a single item measure developed to assess drug use in primary care.²⁶ We will measure frequency, type and quantity of exercise using questions from the National Health Interview Survey.
- ❑ *Comorbidities.* We will assess baseline comorbid conditions using the survey version of the Charlson index.²⁷

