To assess the impact of non-ignorable survey non-response, or missing not at random non-response, we will implement pattern-mixture analyses. Using content expertise and the observed missing data patterns, we will develop these pattern-mixture models. The nature of these models is difficult to specify in advance of observing the different patterns but we will posit distributions for the missing data. For each set of posited distributions and the observed data, we will calculate revised estimates for the relevant intervention effects. One potential model would be to use the propensity stratum derived in the analysis described above and, within each stratum build a distribution for the outcome of interest by shifting the observed distribution among the responders. Content expertise and empirical results will be used to determine the form and magnitude of shift. These distributions would then be used to impute values for the non-responders to cotinine validation in the imputation process described immediately above. Variations of this approach and other approaches will be used to assess the sensitivity of the analyses above to non-ignorable non-response.

We will be enrolling patients after they complete the baseline survey, which maximizes our internal validity; thus we will have baseline data on all participants. The methods above for imputing missing data address the issue of non-response to all or part of either the 6-month or 12-month survey and cotinine validation. We will have limited data available on those who do not respond to the baseline survey, but we will use what data we have to compare initial responders to non-responders, in order to address external validity.

Specific aim analysis

The data will first be summarized numerically using descriptive statistics and frequency distributions examined for validity. Comparison of the baseline demographic and tobacco use characteristics between the two treatment groups will be performed using chi-square tests for categorical data and t-tests or nonparametric tests for ordinal or continuous data.

Aim 1: Compare the reach and efficacy of a proactive outreach telephone-based tobacco cessation (PRO) program for patients seen in mental health to usual care (UC) advice and referral to local VA and community tobacco cessation resources.

H1: Compared to the control group, the proactive intervention will increase the smoking abstinence rate at 12 month follow up.

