Method: The study design is a randomized block design with the blocks comprising combinations of the four hospital sites.

We will address the question of Reach via two indices:

- Proportion of patients who respond to the outreach letters and enroll in the study (i.e., completed the baseline survey). This analysis will help us understand the proportion of smokers in Mental Health who will respond to proactive outreach. Given the innovative nature of the proactive outreach approach, we will examine the acceptability of the intervention to determine which patients are more likely to accept treatment in the PRO and UC conditions. Specifically, we will use multivariable logistic regression to determine which baseline characteristics (e.g., age, race/ethnicity, income, mental health diagnosis, symptom severity) are associated with receipt of cessation counseling (state quitline or VA) or use of cessation medications.
- Proportion of patients who engage in at least one treatment session compared to control patients. Specifically, we will determine how many patients in the intervention arm used treatment (counseling and/or medications) and compare this to the number of patients

enrolled in the control arm who report using existing VA tobacco cessation services on the follow-up surveys, which will provide data regarding acceptability of treatment.

The primary smoking outcome variable that is expected to be affected by treatment is dichotomous cotinine-validated abstinence at 12 months post-enrollment. The comparisons of the abstinence rates across the two groups will be made using exact logistic regression methods, accounting for stratification by site, to model the log odds of use of smoking cessation treatment and log odds of 12-month abstinence. Exact logistic regression employs the non-parametric Chi-square test or Fisher's exact test.³⁵ These tests are widely applicable in complete randomized experimental designs that yield contingency tables. Fisher's exact test is particularly suitable for contingency tables with small and unbalanced frequency counts, which are to be expected for the population-based outcome we have chosen where our population quit rate in the control condition is expected to be 4%.

Aim 2: Model longitudinal associations between baseline sociodemographic, medical and mental health characteristics and validated abstinence at 6 and 12 months in the PRO and UC conditions.

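### Six of the eight Aim 2 covariates treated as baseline are listed only under a mailed 2-week survey, and the plan states no method for participants who do not return it

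*Combined protocol and SAP*

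**What the plan says.** Returning the baseline survey enrolls a participant (Section 5.4), and randomization follows (Section 5.5). Section 6.0, Missing Data, concludes from this order that "thus we will have baseline data on all participants".

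Section 5.7.1 gives the baseline survey four topics: smoking history, covering "number of cigarettes smoked per day, number of days smoking per week, and nicotine dependence"; motivation ("We will assess readiness for change using the Stage of Change scale"); tobacco treatment in the prior year; and one general-health item.

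Section 5.7.2 places the rest on the 2-week survey. On demographics: "Age, sex, marital/partnership status, race/ethnicity, education, and occupation will be assessed". On self-efficacy: "Self-efficacy for smoking cessation will be measured with the 14-item Confidence Questionnaire Form". Alcohol and drug use, comorbidity and the two psychological distress scales are also listed there.

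Section 5.7 sends the surveys after baseline "by mail 2 weeks after enrollment, and by telephone (or mail for non-respondents) at 6 and 12 months from enrollment". The ten telephone attempts and the change of mode are described for the 6- and 12-month surveys only. Section 5.7.3 does not repeat the sociodemographic items.

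Section 6.0 says its imputation methods "address the issue of non-response to all or part of either the 6-month or 12-month survey and cotinine validation". The procedure it describes draws a value for the outcome. Its reach regression names example predictors ("e.g., age, race/ethnicity, income, mental health diagnosis, symptom severity"), and its Aim 2 method names eight patient-level baseline covariates.

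**The concern.** The analysis section treats as baseline several variables that a participant can be randomized without ever supplying. The documents blur the two surveys elsewhere too. Section 5.7.2 describes the comorbidity measure as baseline, and Section 5.6 says the mental health provider is identified on the baseline survey although that question is listed under the 2-week one. This may be why non-response to the 2-week survey was not planned for.

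At stake are Aim 2 and the reach regression. Both H2 predictors, mental distress and active substance abuse, are 2-week items. Logistic and mixed models by default drop records with a missing covariate, and the plan states no alternative. Counselors phone intervention participants within a week of receiving the baseline survey (Section 5.6), so 2-week response comes after assignment and possibly after treatment contact. If response depends on arm or engagement, restricting the model to responders could distort the Aim 2 treatment and treatment-by-time terms and the predictors of uptake. Repeat measures at 6 and 12 months come after treatment and cannot stand in for baseline values.

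**Working it through.** **1. The plan's own figure.** Inputs from Section 6.0, Power calculations: 1,920 per group, control rate 4%, two-sided alpha 0.05, 20% uptake, 16% quit rate among those counseled.

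- Intervention rate: 0.20 × 0.16 + 0.80 × 0.04 = 0.064.
- Power = Φ{[|p2 − p1| − 1.96·√(2p̄(1 − p̄)/n)] / √([p1(1 − p1) + p2(1 − p2)]/n)}, with p̄ = 0.052 and n = 1,920.
- This is Φ{(0.024 − 0.01405)/0.00716} = 0.918, or 0.906 with a continuity correction.

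The stated 90% is reproduced. The point disputes no figure in the power section.

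**2. Where each named covariate is collected.**

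| Covariate | Listed survey or extract |
|---|---|
| Nicotine dependence (Aim 2) | Baseline survey |
| Motivation (Aim 2) | Baseline survey |
| Age (Aim 2, reach) | 2-week survey |
| Sex (Aim 2) | 2-week survey; also held in the record, since Section 5.3 samples by sex |
| Race/ethnicity (Aim 2, reach) | 2-week survey |
| Self-efficacy (Aim 2) | 2-week survey |
| Mental distress / symptom severity (Aim 2, reach) | 2-week survey |
| Substance use (Aim 2) | 2-week survey |
| Mental health diagnosis (reach) | Electronic record (Section 5.7.5) |
| Income (reach) | No survey description or record extract |

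Aim 2: 6 of 8 are listed only under the 2-week survey. Taking sex from the record leaves 5, and taking age as well leaves 4. Reach examples: 3 of 5 are 2-week items, or 2 of 5 if age comes from the record, and income has no listed source.

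**3. Scope of the imputation.** The procedure imputes the outcome within arm and site strata. The stated scope is the 6-month survey, the 12-month survey and cotinine validation. No rule covers a missing 2-week covariate.

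**4. Illustrative size.** The documents give no 2-week response rate r, so r is an assumption. Assume also complete-case fitting and loss unrelated to outcome and equal in both arms.

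- Expected abstainers: 1,920 × 0.04 + 1,920 × 0.064 = 76.8 + 122.9 = 199.7.
- Participants kept = 3,840 × r; abstainers kept = 199.7 × r; standard-error factor = 1/√r.
- The last column applies the step 1 formula with n = 1,920 × r. It is an unadjusted 4% versus 6.4% contrast, given for scale, and is not the power of the Aim 2 model.

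| Assumed r | Participants kept | Abstainers kept | SE factor | Power, 4% vs 6.4% |
|---|---|---|---|---|
| 95% | 3,648 | about 190 | 1.03 | 0.90 |
| 90% | 3,456 | about 180 | 1.05 | 0.89 |
| 80% | 3,072 | about 160 | 1.12 | 0.85 |
| 70% | 2,688 | about 140 | 1.20 | 0.80 |
| 60% | 2,304 | about 120 | 1.29 | 0.74 |
| 50% | 1,920 | about 100 | 1.41 | 0.66 |

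Some 2-week non-responders will also lack the 12-month outcome. The table therefore shows loss from the full randomized set, not loss on top of outcome non-response.

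**The case against.** The strongest defense is that the quoted sentence is true as written. It contrasts enrollees with people who never returned the baseline survey, and every enrollee has that survey. This stands: a reader might infer that the sentence is false, but the documents do not support that. The fault is that later text relies on the sentence for variables it does not cover.

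Second, a reader might infer that all six variables are lost for non-responders. Sex is used for sampling, and Section 5.9 limits the study to people over 18, so age is presumably held as well. This stands in part. No section says either will be taken from the record for analysis, and four covariates, including both H2 predictors, remain dependent on the 2-week survey in any case.

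Third, the plan never prescribes complete-case analysis, and it commits in general terms to multiple imputation that uses baseline information and partial later surveys. Dropout of non-responders is therefore an inference from software defaults and from the outcome-only procedure. It is a reasonable inference, but it should be stated as one.

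Fourth, a \$10 payment accompanies each survey, and 2-week response may be high. At 95% the precision loss is only about 3%. A rule for missing covariates would still be needed.

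Fifth, the reach predictors are examples, and the survey instruments are not in the documents. Income should therefore be described as not listed, rather than as certainly not asked.

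**Conclusion.** The point holds for Aim 2 and the reach regression. Complete data are assured only for baseline-survey items. Six of eight Aim 2 covariates are listed under a later mailed survey, four of them still depend on it if age and sex are taken from the record, and no method is stated for their absence.

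The size is unknown because no response rate is given. At an assumed 50% to 95%, complete-case models would keep 1,920 to 3,648 of 3,840 participants and about 100 to 190 of about 200 expected abstainers, with standard errors about 41% to 3% larger.

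Two stronger readings are not supported. A reader might infer that the Aim 2 treatment effect is biased. The timing makes differential loss possible, but nothing in the documents shows that it occurs, its direction or its size. A reader might also infer that the primary result is at risk. The 12-month comparison adjusts only for site, so it is not affected by this route. The exception would be if the baseline characteristics in the outcome-imputation propensity model include 2-week items, which the plan leaves open.

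The change is worth making, but it concerns the secondary analyses.

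**What to change.** 1. Take age, sex and race/ethnicity for all 3,840 participants from the electronic record. The cost is a few more fields in an existing extract. Recorded race/ethnicity can differ from self-report, and the administrative data listed in the Section 5.9 table may need updating.
2. Extend the multiple imputation in Section 6.0 to missing 2-week covariates, within arm and site, using record and baseline-survey data and including the analysis outcomes in the imputation model. State that Aim 2 and the reach regression use all randomized participants. Say also whether 2-week items enter the propensity model for the primary outcome. The cost is a larger imputation model that rests on a missing-at-random assumption. It will recover little precision for the distress and substance-use coefficients themselves; the main gain is that the treatment terms refer to everyone randomized.
3. Reword the Missing Data sentence to say that only baseline-survey items are complete for all participants.
4. Name a source for income or remove it from the reach predictors.

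None of this needs new patient contact. Telephone follow-up of 2-week non-responders, or moving items to the baseline survey, is not recommended. The first adds staff work. The second would come after recruitment has begun (the power section already cites first-quarter response rates), so early enrollees would still lack the items.
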